## **Introduction**

The 2010 Census indicates that 19.3% of the U.S. population, or approximately 60 million people, reside in rural areas (1). Obesity prevalence in both children (2-4) and adults is significantly higher in rural compared with urban residents (5-8), and approaches 40% in rural adults (6, 7). Rural residents are less physically active (5, 6, 8), consume less healthy diets (5, 9), and have higher rates of obesity associated health problems (10-13), and all-cause mortality (6) compared with their urban counterparts. The Rural Healthy People 2020 survey of 1,214 rural health stakeholders indicated that nutrition and weight status ranked second behind access to health care as important rural health priorities (14).

Barriers to weight management for rural residents include limited availability of programs/professionals trained in weight management (6, 15, 16), and travel distance/expense to attend on-site programs (17) in areas with limited or non-existent public transportation (18). Healthy foods are less available and affordable in rural areas (19-21) requiring travel to urban areas where fresh produce, and less expensive foods are available (22, 23). Roads designed for higher speed traffic (24, 25), few sidewalks (26, 27) and limited availability of fitness facilities or parks (21, 28, 29) make rural areas less conducive to physical activity (PA).

Rural health clinics offer a potential venue for delivery of weight management to rural residents. However, traditional, on-site individual or group-based programs (30) require travel to a clinic for weekly face-to-face meetings, and are therefore impractical and/or inconvenient for rural residents. Rural clinics are unlikely to employ staff with the requisite expertise to provide effective weight management. Thus, weight management in rural clinics is generally limited to brief physician counseling and/or referral to a registered dietitian to assist patients with complying to an energy reduced diet and increased PA; an approach which is minimally effective (30-32).

Our research team has demonstrated the effectiveness of weight management delivered by university-based health educators via group conference (6 mos. =-10.3%, 18 mos. = - 7.4%) (33, 34), or individual phone (IP) calls (6 mos. = -10.5%) (35) to both urban and rural adults. Weight loss with the group phone (GP) intervention was equivalent to an identical intervention delivered in a traditional on-site group meeting format (34). Telephone delivery eliminates the need for travel to on-site meetings (17). Group phone delivery allows participant interaction which has the potential to increase accountability, social support, and rapport, and has also been associated with reduced drop-out (36) and improved weight loss (37, 38). Group-based interventions may be especially desirable for rural residents who are often socially isolated (39), while the IP approach allows participant anonymity, that some may prefer.

Thus, effective weight management can be achieved when interventions are delivered by university-based health educators using GP or IP approaches. However, the comparative effectiveness of GP and IP interventions, when delivered by rural clinic associated personnel, e.g., nurses, nurse practitioners, physician assistants, or community health professionals trained by our research team, has not been evaluated, and will be the focus of this trial.

## **Methods and Materials**

### **Study Overview**

Health care providers at five primary care clinics, or community health professionals serving individuals in rural Kansas, will be trained to deliver the GP and IP interventions and an

enhanced version of usual care to compare weight loss (0-6 mos.), weight maintenance (7-18 mos.), and weight change during a 6 mo. period of no contact (19-24 mos.) between interventions. The GP and IP interventions will be identical with the exception of the format (group vs. individual) and duration of contact, i.e., GP (~45 min/session) vs. IP (~15 min/session). Usual care, which is generally limited to brief counseling (5-7 min.) during a routine physician visit and/or referral to a registered dietitian (40), will be enhanced by increased contact with the health care providers and provision of information regarding community assets for increased PA and improved nutrition. We considered using an established weight management intervention such as the Diabetes Prevention Program or Look AHEAD protocols (41-43) as a comparison group. Although efficacious in some settings, the delivery of these interventions is expensive and burdensome for both participants and providers, and are unlikely to be tolerated by rural clinics. Following considerable discussion, we decided to compare our GP and IP interventions to an enhanced version of weight management as currently practiced in rural primary care clinics (40), i.e., enhanced usual care (EUC). Two hundred overweight/obese adults will be randomized in a 2:2:1 allocation to the GP (n=80), IP (n=80), or EUC (n=40) arms. Outcomes will be assessed by the research team at baseline (0 mos.), following weight loss (6 mos.), during weight maintenance (12 and 18 mos.) and after a 6 mo. no-contact period (24 mos.). The primary aim is to compare weight change at 6 mos. between the 3 interventions arms; GP, IP, and EUC, analyzed using intention-to treat principles. Secondarily, we will compare the following across the three interventions groups: 1) weight at 12, 18 and 24 mos. 2) metabolic syndrome risk factors (waist circumference, triglycerides, HDL-cholesterol, blood pressure, fasting glucose) at 6, 12 and 18 mos. Cost, cost effectiveness, and contingent valuation analysis and extensive process evaluation will also be completed. Approval for this study has been obtained from the Human Subjects Committee at the University of Kansas-Lawrence.

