### **Statistical power and analysis**

**Statistical power.** Differences in weight loss at six mos. between participants randomized to the IP or EUC, and GP or IP are of primary interest. We hypothesize that six month weight loss will average 2 kg, 8 kg, and 12 kg in the EUC, IP, and GP arms, respectively, with a common standard deviation for weight change of 7 kg (34) (35). Statistical power was determined assuming a type 1 error rate of 2.5% for each of our two primary comparisons. Based on these assumptions, randomization of 200 participants with a 2:2:1 allocation; GP (n=80), IP (n=80), EUC (n=40) will provide 98% power to detect significantly greater weight loss in IP versus EUC, and 91% power to detect significantly greater weight loss in GP versus IP. The global F-test for a one-way ANOVA provides greater than 99% power under these assumptions. The primary analysis will be intent-to-treat with imputation of missing data using multiple imputation techniques. However, a completers only analysis, with a 20% loss to follow-up, will still provide 95% power for the IP-EUC, and 83% power for the GP-IP comparisons.

**Analysis plan.** A global one-way ANOVA will be followed with two pairwise t-tests on the two comparisons of interest, IP versus EUC, and GP versus IP. Statistical significance for each pairwise comparisons will be  $p \leq 0.025$ ; however, all other analyses will be conducted at  $p < 0.05$ . These primary analyses will be intent-to-treat utilizing multiple imputation for missing data and to determine corresponding  $p$ -values. In addition to the intent-to-treat analysis, a completers only analysis will be performed, i.e., participants with weight at 6 months. Secondarily, we will compare weight between the three study arms across 24 months using a mixed linear model,

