assuming an autoregressive correlation structure of weight over time, controlling for baseline weight, treatment group and time as covariates. The global comparison across the three arms will be followed by two pairwise comparisons of interest, i.e., IP versus EUC, and GP versus IP. Independent comparisons of change in each chronic disease risk factor, i.e., waist circumference, triglycerides, HDL cholesterol, blood pressure, and fasting glucose at 6, 12, and 18 mos., across the 3 intervention arms will be completed using a mixed linear model, assuming an autoregressive correlations structure. We will also compare Quality of life (SF-36), daily stress associated with eating (Nutrition Hassles Questionnaire), self-efficacy for weight change (WELS), self-efficacy for exercise (EXES), and self-efficacy for overcoming barriers to exercise (BARSE) among the three intervention arms across 24 months using a using a mixed linear model assuming an autoregressive correlation structure both unadjusted and adjusted for covariates. A variety of exploratory analyses, as deemed appropriate by the principal investigator and the project biostatistician, e.g., assessment of the impact of health educator absences and turnover, community environment for healthy eating and PA etc. on weight loss outcomes, will be performed. Analyses will be completed using SAS version 9.4 or higher.

**Missing data.** We will determine if the proportion of participants lost to follow-up differs by intervention arm and/or sex, and compare demographic characteristics between those lost to follow-up and completers. If there are differences across treatment groups, we will examine demographic characteristics, i.e., sex, age, magnitude of weight loss, between completers and those lost to follow-up, to determine if there are significant differences ( $p < 0.05$ ) in those characteristics. If missing data are related to intervention group and/or demographic characteristics, we will use model based multiple imputation; otherwise, traditional multiple imputation will be used.

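### GP versus enhanced usual care has no pre-specified pairwise test, so it can be concluded only if both named comparisons succeed

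*Combined protocol and SAP*

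**What the plan says.** The Study Overview sets a three-arm primary aim: "The primary aim is to compare weight change at 6 mos. between the 3 interventions arms". It also explains the control arm. Having considered established programmes as comparator, the investigators write that "we decided to compare our GP and IP interventions to an enhanced version of weight management as currently practiced in rural primary care clinics". Both phone arms are therefore meant to be judged against EUC.

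The section on statistical power and analysis is narrower. It states that "Differences in weight loss at six mos. between participants randomized to the IP or EUC, and GP or IP are of primary interest" and assumes "a type 1 error rate of 2.5% for each of our two primary comparisons". The primary analysis reads: "A global one-way ANOVA will be followed with two pairwise t-tests on the two comparisons of interest, IP versus EUC, and GP versus IP". For weight over 24 months the same pairs return: "The global comparison across the three arms will be followed by two pairwise comparisons of interest, i.e., IP versus EUC, and GP versus IP".

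Nowhere is GP versus EUC named as a test, given a significance level or given a power. The plan also does not say whether the global test must be significant before the pairwise tests are read.

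**The concern.** One of the two comparisons for which the EUC arm exists has no planned pairwise test. The global F-test involves GP and EUC but does not say which arms differ.

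The only confirmatory route to GP being better than usual care is a chain: IP beats EUC and GP beats IP. Both links must hold. If IP beats EUC and GP does not differ significantly from IP, nothing confirmatory follows about GP against EUC, because a non-significant GP–IP test does not show that the two are equivalent.

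The trial could then end with a formal conclusion for IP and none for GP, the arm with 80 participants and the largest hypothesised loss. A GP–EUC test added after the results are known would be post hoc.

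**Working it through.** **Inputs.** From the power section: mean 6-month losses GP 12, IP 8, EUC 2 kg; SD 7 kg; 80/80/40 randomised; 0.025 per named comparison; 20% loss to follow-up, giving 64/64/32 completers. From the Introduction: earlier 6-month losses of 10.3% (group phone) and 10.5% (individual phone). The plan does not state sidedness. Two-sided tests reproduce all its pairwise powers. One-sided tests do not (GP–IP would be 94.9%, not 91%).

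**Step 1. Reproduce the plan's power.** SE = 7 × √(1/n₁ + 1/n₂), λ = difference / SE, and power is the probability that |t| with noncentrality λ exceeds its two-sided 0.025 critical value.

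- IP–EUC: SE = 7 × √(1/80 + 1/40) = 1.356; λ = 6/1.356 = 4.43; power 98.4% (plan: 98%).
- GP–IP: SE = 7 × √(1/80 + 1/80) = 1.107; λ = 4/1.107 = 3.61; power 91.0% (plan: 91%).
- Completers: 95.2% and 83.1% (plan: 95% and 83%).

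The stated figures are right.

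**Step 2. Power of the missing comparison.** GP–EUC: difference 12 − 2 = 10 kg; λ = 10/1.356 = 7.38; power above 99.9% at 0.05, 0.025 or 0.0167, and also at 64 versus 32.

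**Step 3. How often the chain breaks under the plan's own means.** P(at least one named test fails) = P(IP–EUC fails) + P(GP–IP fails) − P(both fail).

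- Full sample: 0.0163 + 0.0895 − 0.0001 = 0.1057; simulation gives 10.5%.
- Completers: 0.0480 + 0.1688 − 0.0014 = 0.2154; simulation gives 21.5%.

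In practically all of these trials a direct GP–EUC test would be significant. Both named tests failing while GP–EUC passes has probability about 0.01% (0.14% for completers).

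**Step 4. Other means (illustrative, not from the documents; SD 7, 80/80/40).** Named tests are at 0.025; GP–EUC is at 0.05 after a significant F.

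- 8/8/2 kg (GP/IP/EUC): IP–EUC passes in 98% and GP–IP in 2.5%. GP–EUC has about 99% power. The chain breaks while GP–EUC is significant in about 97% of trials.
- 7/5/2 kg: powers are 48% (IP–EUC), 33% (GP–IP) and 91% (GP–EUC). Both named tests fail in 29% of trials, and both fail while GP–EUC is significant in about 21%.

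The observed differences show how both links can fail. At SD 7, IP–EUC misses significance below 3.08 kg and GP–IP below 2.50 kg. Both can therefore miss with an observed GP–EUC difference of up to 3.08 + 2.50 = 5.58 kg, where t = 5.58/1.356 = 4.12 and p = 0.00007.

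**Step 5. Power if the third comparison is added (plan's means).**

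| Rule | Sample | IP–EUC | GP–IP | GP–EUC |
|---|---|---|---|---|
| Two tests at 0.025 (plan) | full | 98.4% | 91.0% | not tested |
| F gate at 0.05, three tests at 0.05 | full | 99.2% | 94.9% | >99.9% |
| F gate at 0.05, three tests at 0.05 | completers | 97.5% | 89.4% | >99.9% |
| No gate, three tests at 0.0167 | full | 97.6% | 88.2% | >99.9% |
| No gate, three tests at 0.0167 | completers | 93.4% | 78.9% | >99.9% |

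With three arms the gated rule holds family-wise error at 5%. If all means are equal, the gate limits false rejection to 5%. If exactly two are equal, only one null hypothesis is true and it is tested at 5%. The simulated rate under the global null was 4.98%.

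**The case against.** The two-pair choice is deliberate. It is stated consistently for 6 and 24 months, it is powered correctly, and it fits an ordered hypothesis (2 < 8 < 12 kg). If both tests succeed in the expected direction, GP better than EUC follows. The Introduction puts the comparative effectiveness of GP and IP at the centre of the trial. All of that stands. It does not remove the mismatch with the Study Overview, which wants both phone arms compared with EUC.

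Four stronger readings are tempting, and the documents do not support them.

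- A reader might infer that the trial is likely to fail both named tests while GP clearly beats usual care. Under the plan's means that is about a 0.01% event. The 21% figure needs effects half those assumed (IP–EUC 3 kg instead of 6, GP–IP 2 kg instead of 4). It also sets GP–EUC at 0.05 against named tests at 0.025: with all three at 0.025 it is about 22.6%, and with all three at 0.05 after the gate it is 9.6%.
- A reader might infer that the three-arm aim is untested. The global ANOVA addresses it; what is missing is the ability to say which arms differ.
- A reader might infer that no statement about GP against EUC is allowed. The plan permits exploratory analyses, so an estimate is not barred. It would lack confirmatory standing.
- A reader might infer that a gated third test is always free. The plan says only that the ANOVA is followed by t-tests, so a gate is a new condition. With GP 4, IP 5, EUC 2 kg (illustrative), IP–EUC is significant at 0.025 but the F-test fails in 3.9% of trials, and IP–EUC power moves from 48.1% to 46.7%.

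**Conclusion.** The point holds as a mismatch between the stated purpose of the EUC arm and the comparisons that are pre-specified. The main risk is a broken chain rather than failure of both tests: about 10.5% under the plan's assumptions, 21.5% among completers, and about 97% if GP and IP lose the same 8 kg.

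The last case is an assumption, but a plausible one. The Introduction's earlier losses for the two formats are nearly equal, although those programmes were delivered by university staff and the power section expects GP to do 4 kg better.

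All figures assume normally distributed changes with a common SD of 7 kg, two-sided tests and independent participants, with no modelling of imputation. The existing tests, their alpha split and their power are internally correct. This is a change the sponsor should make, not a flaw that invalidates the primary analysis.

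**What to change.** Add GP versus EUC as a pre-specified pairwise comparison at 6 months and in the 24-month weight model, before outcomes by arm are examined. State that the global F-test at 0.05 is a gate and that, if it is significant, all three pairs are tested at 0.05. Replace the power statement with about 99% (IP–EUC), 95% (GP–IP) and over 99.9% (GP–EUC); for completers about 97%, 89% and over 99.9%.

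The cost is a short rewording of the analysis and power paragraphs and one extra contrast, with no new participants or data. The decision rule and significance level for the two existing comparisons do change, and the gate can cost IP–EUC a little power if effects are small and not ordered as hypothesised.

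If the sponsor prefers no gate, three tests at 0.0167 are a valid alternative: about 97.6%, 88% and over 99.9%. Relative to the present plan this lowers GP–IP power by about 3 percentage points (91.0 − 88.2 = 2.8).

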### **Clinic recruitment**

At least five clinics, located in rural areas, and/or serving primarily rural residents, with a census of ~4,000 to 8,000 patients will be asked to participate. A universally recognized classification scheme or definition for urban/rural areas does not exist (44-46). For this project we will use the U.S. Census Bureau definition which states: “Rural is defined as all population, housing, and territory not included within an urbanized area or urban cluster” (47). An urbanized area is defined as a population of 50,000 or more, and urban clusters are areas with populations of at least 2,500, but less than 50,000. Each clinic will be asked to assist with recruitment of 40 participants, deliver the interventions and provide space for both outcome assessments and delivery of the EUC intervention arm.

### **Participant eligibility**

To enhance generalizability of the results, individuals with chronic medical conditions, or common risk factors such as hypertension, tobacco use, hyperlipidemia, diabetes mellitus, etc., who receive clearance from their primary care physician, will be allowed to participate. These individuals are representative of those typically seeking weight management, and that have participated in our previous trials demonstrating the effectiveness of both the GP and IP interventions (34, 48). Medical conditions and medication use may be considered potential confounders; however, randomization should ensure that health status will be similar across study groups. In addition to requiring primary care physical approval, additional inclusion and exclusion criteria (Table 1), and a comprehensive medical management plan have been developed to protect the participants in this trial. Weight loss in high risk participants, i.e., those with chronic conditions or using prescription medications, will be monitored by both the health educators and the study physician. Participants will be asked to report changes in medications

and/or adverse events to the health educators, via toll-free phone call, fax, or email, as they occur.

### **Recruitment/randomization**

In addition to recruitment by rural clinic personnel, we will also recruit using flyers posted in rural communities and media advertising including print, radio and Facebook®. We will recruit at least 50% females and minorities to reflect or exceed minority representation in rural Kansas (16.7%) (49). Potential participants will be asked to contact study staff via phone, email or our laboratory web site. Interested individuals will be directed to complete a brief web-based screener on our laboratory website, or will be interviewed by phone, to assess self-reported height and weight (BMI), medication use, presence of chronic disease, smoking habits, previous attempts at weight loss, and current level of PA. Those satisfying the initial eligibility criteria will be scheduled to attend an in-person meeting with study staff at the participant's respective clinic. At this session staff will describe the project, answer questions, obtain consent, complete eligibility screening surveys, and measure height and weight to determine preliminary eligibility based on BMI. Screening surveys including health history, depression, eating behavior and binge eating will be administered using web-based software (Research Electronic Data Capture software (REDCap), Vanderbilt University, Nashville, TN) (50). These surveys will be completed during the in-person meeting or at home, depending on the availability of home internet access. Project staff will then send a form (fax/email) to the potential participant's primary care physician describing the study and requesting clearance for participation. Final eligibility based on BMI will be confirmed at baseline testing, using height and fasting weight assessed with participants wearing hospital gowns. Participants in each clinic will be randomized, stratified by sex, to one of the three study arms. The randomization sequence will be generated by an independent statistician, sent to the project coordinator and concealed until intervention groups are assigned.

### **Community assessments-Physical activity/healthy eating**

Prior to initiating the intervention we will evaluate environmental facilitators/barriers to both PA and healthy eating in the area surrounding each participating clinic. The Rural Active Living Assessment tools which include The Street Segment Assessment, Town-wide Assessment, and The Town Program and Policy Assessment (51) will be used to assess the built environment, town characteristics, community programs, and policies and resources that can influence PA. Facilitators/barriers to healthy eating will be based on surveys with both clinic health professionals and patients. Food availability will be assessed using a validated survey developed for the Multi-Ethnic Study of Atherosclerosis to measure perceived availability of healthy food options and access to food shopping in an individual's neighborhood (52, 53). Information gathered related to the PA or healthy eating environment will be used to tailor our intervention to each participating clinic.

## **INTERVENTION**

**Health educator selection/training.** Our research team, in collaboration with clinic/health system management, will select a staff member with an interest in delivering weight management, e.g., nurse, nurse practitioner, physician's assistant, registered dietitian, exercise physiologist, or a qualified professional from the local community, e.g. registered dietitian, certified diabetes or health educator, to serve as health educator. Participating clinics, or community professionals will be compensated for time devoted to this project. The selected health educator in each clinic will deliver all three interventions, i.e., GP and IP, and EUC, to minimize the potential for health educator effects. Health educators will be provided with a detailed intervention notebook which outlines the topics for each session, provides answers to common participant questions, and strategies for engaging participants in the intervention.

Health educators will be trained by our research team during an initial one-day, on-site session at each clinic, and four one-hour sessions conducted via FaceTime® prior to initiating the intervention. On-site training will provide an overview of the intervention notebook, discuss the biologic/medical impacts of weight loss and strategies for effective intervention delivery via GP or IP calls, or face-to-face that will be utilized in the EUC arm. Audio recordings from GP sessions from our completed NIH trial which compared GP and face-to-face delivery of weight management (34) will be utilized to demonstrate effective leadership and facilitation techniques in the GP setting. Strategies for conducting IP and face-to-face interventions will be demonstrated by role playing with a member of our research team with the health educator and clinic staff as participants. The four follow-up training sessions will be used to reinforce strategies taught during on-site training and to further model teaching strategies used in GP, IP and face-to-face sessions. Prior to initiating the intervention all health educators will be required to successfully conduct three simulated sessions of each of the three intervention arms, i.e. GP, IP, and EUC in which members of the research team will serve as participants. A standardized checklist, including the important skills/strategies taught during training, will be used to assure all health educators demonstrate mastery of these skills. The research team will be available for consultation with health educators to address issues that may arise during the interventions.

**Theoretical model.** The intervention will be grounded in Social Cognitive Theory, a triadic, dynamic model that indicates an individual's behavior is uniquely determined by the reciprocal interaction of personal, behavioral, and environmental factors, to effect change in energy intake (EI) and PA (54, 55). We will focus on social cognitive techniques which have been shown to be most effective for changing EI and PA including intention formation, goal setting, self-monitoring (diet, PA, weight), and participant feedback relative to intervention compliance (56). These techniques will be enhanced by employing behavior shaping (gradually modifying diet and PA), social support, and stimulus control (strategies to decrease cues for less desirable and increase cues for more desirable diet and PA behaviors). Additionally, cognitive strategies will be used to increase self-efficacy and to deal with social relationships affected by weight, such as identifying/confronting self-sabotage attempts, responding to stress with non-food techniques, relapse prevention strategies to teach participants to recognize precursors and consequences of lapses, and develop plans for addressing high risk situations. The intervention is also informed by both social ecologic (57) and social network theories (58) as content will be tailored to both the physical and social environment of participants.

**General Description.** All intervention arms will complete weight loss (6 mos.) and weight maintenance (12 mos.). Weight will also be evaluated following a 6 mos. no contact follow-up. A comparison of contact format and intervention session frequency and duration between intervention arms is shown in Table 2. The protocols for reducing EI, increasing PA, content presented during behavioral sessions, and self-monitoring diet, weight, and PA will be identical in the GP and IP arms. Participants in both the GP and IP arms will receive identical notebooks that will include detailed instructions for the weight loss and weight maintenance diets including recipes, instructions for PA, self-monitoring diet and PA, and the schedule for behavioral sessions. The notebooks will be organized by behavioral session and contain handouts, worksheets, and assignments specific to each session.

